10.2 Analysis of the primary endpoint

Change in bladder appearance (mucosa post- and pre-catheterization) translated into a grading scaled from 1-4 will be analysed in a mixed model with treatment (comparator and investigational device) as fixed effect.

Treatment differences as well as 95% confidence intervals will be estimated by using Proc Mixed in SAS.

10.3 Analysis of exploratory endpoints

All exploratory endpoints i.e., RBC and WBC will be presented by descriptive statistics.

10.4 Sample size

As this is an exploratory study no formal sample size calculation has been performed. It is assumed that a total of 40 completers i.e., 20 completers (a minimum of 18 completers needed) in each group (MHC and 2EC) will be adequate for obtaining indications on differences in eyelet associated trauma during bladder emptying with either a MHC or a 2EC.

10.5 Level of significance and power

A two-sided significance level of 5% will be applied. For a description of the power see section 10.4 above.

10.6 Pass/fail criteria

As this is an exploratory investigation with no prior experience, any result will provide valuable insight into how catheter design affects the bladder mucosa in the clinical setting.

11 Data management

11.1 Data collection and data management

11.1.1 Data Collection in the clinical investigation

Data management and statistical analyses are carried out by Medical Affairs, Coloplast A/S.

Data will be collected through an electronic data capturing (EDC) system on electronic Case Report Forms (eCRF), a secure, internet-based case report form. This system will be used to record all subject information collected in the investigation for secure data tracking and centralised data monitoring ("remote monitoring") done by monitors, as defined in the monitoring plan.

The EDC system used is Rave EDC, version 2020.3.2, delivered by Medidata Solutions Inc. The system is designed to be compliant with the FDA requirements of 21 CFR part 11. It is a validated data management system allowing only qualified and trained personnel to enter the system. The system has full audit trail and electronic signature.

The sponsor will be responsible for training the Principal Investigator, or designee, in completion of the eCRF.

Principal Investigator, or delegate, at the clinical site will perform primary data collection directly into the eCRF or drawn from source document (medical records) reviews. The eCRF will be completed on a continuous basis starting from the point of enrolling the subject to final follow up.

The eCRF will be completed by the investigator, or delegate, who have signed the Site Personnel Signature and Delegation List and Clinical Investigation Training Log. It will be the responsibility of the Principal Investigator, or designee, to ensure that all measurements and observations are correctly noted in the eCRF.

All assessments and observations throughout the investigation for each subject must be carefully recorded in an eCRF during the visit or immediately after. The eCRF makes it possible to enter data right away when they are obtained. This is the preferred way of collecting data. In case this is not possible the data should be entered no later than 5 days after the visit / procedure.

Adverse events should be registered following the timelines described in the Adverse Event section.

The cystoscope images will be uploaded to a secure environment.

In the unforeseen situation, where site cannot establish connection to the EDC system a paper CRF (pCRF) has been printed and supplied by sponsor.

The Principal Investigator will keep a separate list of the subjects' ID numbers, enrolment date, randomisation number, date of birth, names, phone number, email and addresses in a locked room/cabinet. Only data referred to in this clinical investigation plan will be recorded in the CRFs.

11.1.2 Database Management, Queries and Quality Control

The data management system has restricted role-based access control. The Principal Investigator, or designee must be trained in the system prior to getting access. The training is web-based and must be completed before

access to the investigation is granted. Training will be documented in the data management system. Only the Principal Investigator, or designee, will be authorised to enter data in the eCRF.

The monitor, using his/her personal login information shall verify all critical data points against the source documents and issue electronic queries for the authorised clinical site personnel to respond, as defined in the monitoring plan.

The Principal Investigator, or designee, using his/her personal login information shall sign each eCRF.

Automated, real time access to the data enable control on study compliance and safety assessments.

A critical quality control will be performed by the sponsor's data management team and queries issued where needed. Such queries will be reviewed by the monitor and must be resolved by the site personnel.

At the end of the study a formal data review meeting will be performed before the database will be locked.

A full audit trail ensures, that each user's (site personnel, monitor, sponsor, data manager) access to and actions in the system is tracked.

The Data Management Procedures are further described in the Data Management SOPs.

11.2 Data retention

All investigation site documents must be archived for a minimum period of 10 years after the final clinical investigation report has been signed. The monitor is responsible for informing the investigator and the CM if this period should be longer for their sites according to local regulation.

12 Amendments to the Clinical Investigation Plan

No changes in the clinical investigation procedures shall be affected without mutual agreement between the Principal Investigator and the sponsor. The agreement of the changes must be documented by signing the corresponding clinical investigation plan amendments and registered in the Change Log.

All significant changes require notification to the EC and applicable regulatory authority. Substantial changes may require approval from the EC and applicable regulatory authority prior to implementation.

13 Deviations from the Clinical Investigation Plan

Deviations to the Clinical Investigation Plan occurs when the activities during the clinical investigation do not comply with the IRB approved investigation plan.

A minor deviation is defined as those that do not increase risk or decrease benefit or do not have a significant effect on the subject's rights, safety, or welfare; and/or on the integrity of the data. If a deviation increases risk or decreases benefit and/or; has a significant effect on the subject's rights, safety, or welfare and/or has a significant effect on the integrity of the data it is defined as a major deviation and the Investigator must inform the monitor immediately, and the Monitor will report and inform the Clinical Manager or designee immediately.

The investigator is not allowed to deviate from the Clinical Investigation Plan unless, under emergency circumstances or to protect the rights, safety, and well-being of the subject(s).

For the purposes of this investigation, any variance from the protocol is considered a deviation and is to be reported.

The site will complete a deviation eCRF for all data-related deviations and all deviations that are not related to the data (for example, an untrained nurse performing study procedures) are reported by the monitor in the periodic monitoring report and any actions for additional follow up are addressed with the Investigator.

If any deviations to the investigation plan are detected during the monitoring visit, the Monitor shall ensure the site reports all deviations in the eCRF or on the Deviation log in the Investigator File. Additionally, the monitor must report any deviation noted during the visit in the Periodic Monitoring Report.

Monitor will align with data management in each investigation, how data management will be informed about all deviations.

Details about the deviation will be collected, for example:

- Site ID
- Subject ID
- Deviation Date
- Clear and concise description of the event
- The reason for the deviation and any corrective action taken, including the date of the corrective action.

If applicable, record the EC notification date and retrieve a copy of the EC Submission Letter for the eTMF.

14 Device Accountability

All access to the investigational devices used in the clinical investigation is controlled by storage procedures and device accountability logs as described below. The investigational devices must only be used in this clinical investigation and only according to the CIP.

Sponsor keeps a device accountability log that states the physical location of all investigational devices from shipment of investigational devices to the investigational sites until return of or disposal.

The PI, or designee, keeps records documenting the receipt, use and return and disposal of the investigational devices, which includes:

- Name of the product received
- Date of receipt
- Identification of each investigational products (batch no./lot no.)
- Number of products received
- Number of products distributed to subject
- The date(s) of use
- Subject identification
- The date on which the investigational product was returned/explanted from the subject
- The date of return unused, expired or malfunctioning investigational products to Sponsor

15 Statement of compliance

The clinical investigation is conducted in accordance with:

- Ethical principles that have their origin in the Declaration of Helsinki, 1964, Last amended at the 59th WMA General Assembly, Brazil, October 2013.
- FDA Regulations
- ISO 14155:2020 "Clinical Investigation of medical devices for human subjects Good clinical practices".

16 Ethics committee and regulatory authorities

The CIP and/or other relevant documents are submitted to the appropriate IRB, if applicable. This clinical investigation will not begin until the required approval from the IRB has been obtained. Any amendment to the clinical investigation plan will be submitted to the same IRB. Sponsor will notify the relevant IRB of the end of the clinical investigation.

17 Data protection

Coloplast will comply with the EU General Data Protection Regulation (GDPR) and the Danish act on data protection ("databeskyttelsesloven"), including in connection with transfer of data to third countries, cf. chapter V of GDPR. Coloplast will only process the subjects' personal data:

- 1. To conduct the investigation and carry out related research based on subject consent (primary use), cf. articles 6(1)(a) and 9(2)(a) of GDPR,
- 2. To comply with applicable legal obligations to e.g., ensure reliability and safety, cf. article 6(1)(c) in conjunction with article 9(1)(i) of GDPR, and
- 3. If separate consent is given for secondary use of subject personal data, cf. articles 6(1)(a) and 9(2)(a) of GDPR carry out research outside the clinical protocol to improve Coloplast's products and services, and for use in education.

Part of Coloplast's processing is carried out on third-party platforms (clinical trial databases) and certain third parties are assisting Coloplast in the processing (e.g., the Principal Investigator, or designee). Such cases will imply a transfer of personal data to the third parties, but solely for the specified purposes and with the third parties acting on instruction from Coloplast. Data may be collected and processed across the Coloplast network, which may entail processing of personal data outside the European Economic Area. In such cases, an adequate level of protection will be ensured by the third parties being subject to the standard contractual clauses on data protection adopted by the EU or to an EU-approved certification mechanism on data protection. For further information about this please the subject can always consult Coloplast's data protection officer (details below).

Subject personal data will be kept as long as required under applicable laws and regulations. The EU Medical Device Regulation obligates Coloplast to keep the data for a period of at least ten years after the investigation is completed, or, in the event that the device is subsequently placed on the market, at least ten years after the last device has been placed on the market. Subject personal data will be deleted at the end of the mandatory retention period.

If the subject has questions or queries regarding Coloplast's handling of personal information, the subject can always contact Coloplast's Data Protection Officer at [contact]. Complaints related to Coloplast's handling of subject personal information may similarly be sent to the Data Protection Officer, and the subject is also entitled to file a complaint with the relevant supervisory authority, which in the case of Denmark is the Danish Data Protection Agency (www.datatilsynet.dk).

The subject can write to [contact] at any time to request:

- Access to personal data
- Correction of errors in personal data or to erase personal data
- Limit what can be done with personal data
- To receive personal data in machine-readable format (data portability).
- Withdrawal of consents the subject has given Coloplast to process personal data

17.1 Indemnity

All subjects are fully covered by Coloplast A/S insurance throughout the investigation.

17.2 Financial conditions

Coloplast A/S will compensate all investigators involved in the clinical investigation for their time and resources spent on the investigation. All financial agreements with the investigation sites involved in the clinical investigation will be specified in a sponsor investigator contract.

18 Informed consent process

Written informed consent is obtained from all subjects participating in the investigation after thorough written and verbal information. The information is given by the investigator or his/her representative in the subjects' native non-technical language. Each subject will be fully informed about the aim of the investigation, procedures, potential risks, or inconveniences and/or expected benefits and ensure ample time is provided before deciding on participation. The subjects will be informed that their participation is voluntary and that they may leave the investigation at any time, without this having any influence on their further treatment.

The informed consent signature form includes personally dated signatures of the subject and the PI, or designee. A copy will be provided to the subject.

If new information is to be given during the investigation, sponsor will inform the investigators, and the new information is given to the subjects by the investigator. If new information becomes available that can significantly affect a subject's future health and medical care that information will be provided to the subject in written form. CM is responsible for writing the information and providing it to investigators that will further provide it to the subjects. If applicable, all affected subjects shall be asked to confirm their continuing informed consent in writing.

This procedure also applies to informed consent obtained from a subject's legal representative. The procedure cannot waive the subjects' legal rights.

19 Subject compensation

[figure not shown]
19.1 Compensation in case of injury

Product liability and No-Fault Clinical Investigation Insurance covering the duration of the clinical investigation are in place, to enable compensation in the event of an injury to a participating subject.

19.2 Compensation for participating in the clinical investigation

If applicable, subjects will be compensated for their participation in the clinical investigation.

Table 19-1 Compensation for subject participation

20 Adverse events, adverse device effects and device deficiencies

20.1 Adverse events

An adverse event is any untoward medical occurrence, unintended disease or injury, or untoward clinical signs (including abnormal laboratory findings) in subjects, users, or other parties, whether or not related to the medical device(s), or the procedures involved. This could include events such as headache or dizziness.

20.2 Adverse device effect

An adverse event, which is related to the use of the investigational medical device, is an adverse device effect, and should be marked as related or possibly related on the adverse event form.

The definition of an adverse device effect includes any event resulting from insufficiencies or inadequacies in the instruction for use, or any malfunction of the medical device, as well as any event resulting from use error or from intentional misuse of the device.

20.3 Device deficiency

A device deficiency is the inadequacy of the investigational device or comparator with respect to its identity, quality, durability, reliability, safety, or performance. This includes malfunctions, use errors and inadequacy in the information supplied by the manufacturer including labelling.

20.4 Serious adverse events (SAE)

A serious adverse event is an adverse event that:

- Led to death,
- Led to a serious deterioration in the health of the subject, users or other persons as defined by one or more of the following:
 - 1. a life-threatening illness or injury, or
 - 2. a permanent impairment of a body structure or a body function including chronic diseases, or
 - 3. in-patient or prolonged hospitalization, or
 - 4. medical or surgical intervention to prevent life-threatening illness or injury or permanent impairment to a body structure or a body function.
- Led to fetal distress, fetal death or a congenital abnormality or birth defect.

This includes device deficiencies that might have led to a serious adverse event if:

- Suitable action had not been taken, or
- · Intervention had not been made, or
- Circumstances had been less fortunate.

These are handled under the serious adverse event reporting.

Planned hospitalization for a pre-existing condition, or a procedure required by the CIP, without serious deterioration in health, is not considered a serious adverse event.

20.4.1 Serious adverse device effect (SADE)

A serious adverse device effect is an adverse device effect that has resulted in any of the consequences characteristic of a serious adverse event.

20.4.2 Anticipated serious adverse device effect (ASADE)

Anticipated serious adverse device effect is any event that by its nature, incidence, severity, or outcome has been previously identified in the risk analysis report.

20.4.3 Unanticipated serious adverse device effect (USADE)

An unanticipated serious adverse device effect is a serious adverse device effect which by its nature, incidence, severity, or outcome has not been identified in the current version of the risk analysis report.

20.5 Medical care of subjects

Principal investigator shall ensure that adequate medical care is provided to a subject experiencing an adverse event during and after participation in the clinical investigation. All serious adverse events will be followed until a resolution is addressed.

The status of all ongoing adverse events is documented during site close-out.

20.6 Reporting and timelines

All adverse events and device deficiencies will be reported in the eDC, Rave database. If, for some reason, the system is off-line, investigators (or designee) are required to report the event to: [contact]

20.7 Investigator's reporting responsibilities

PI at each site must assess all (S)AE's that occur at his/her site.

All serious adverse events and serious adverse device effects must be reported to sponsor within 24 hours of the site becoming aware of the event.

A device deficiency that could have led to a serious adverse event but did not because suitable action was taken, intervention had been made or because of fortunate circumstances should be reported to sponsor within 24 hours of the site becoming aware of the event.

New findings and/or updates in relation to already reported serious events should also be reported to sponsor within 24 hours of the site becoming aware of the event.

Device deficiencies and all adverse device effects must be reported to sponsor within 10 days of becoming aware of the event.

When reporting the SAE, the relationship to the test material shall be described whether the event is considered:

- Not related, the event has no temporal relationship with the use of the test material or the procedures.
- Unlikely related, the relationship with the use of the test material seems not relevant and/or the event can be reasonably explained by another cause, but additional information may be obtained.
- Possibly related, the relationship with the use of the test material is weak but cannot be ruled out
 completely. Alternative causes are also possible (e.g., an underlying or concurrent illness/ clinical
 condition or/and an effect of another device, drug, or treatment). Cases where relatedness cannot be
 assessed, or no information has been obtained should also be classified as possible.
- **Probably related**, the relationship with the use of the test material seems relevant and/or the event cannot reasonably be explained by another cause, but additional information may be obtained.
- **Definitely related/Causal relationship,** the event has a temporal relationship with the test material use/application or procedures.

The investigator will assess intensity for each AE and SAE reported during the investigation and assign it to one of the following categories:

- Mild, the intensity of the event is mild with no further action or intervention
- Moderate, the intensity of the event will lead to an action or intervention to solve the event
- Severe, the intensity of the event will lead to follow up on the action or intervention, as the effect of the action or intervention may not decrease the symptoms.

All above events must be reported by use of the relevant adverse event/serious adverse event/device deficiency form.

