This investigation is a randomized, single-blinded, parallel, single-center investigation. In total, up to 50 subjects (40 completers) will be included and each subject will have two test visits overseen by the Principal Investigator (PI), or designee. Each subject will be enrolled in the investigation, which can be up to 3 days (if Day 0 and Day 1 are not on same day). The subjects will be randomly assigned to test either the test product or the comparator product, with at least 20 subjects assigned to each product."

Expected duration of the clinical investigation:

The investigation will be conducted from November 2021 through February 2022.

Endpoints & Assessments:

Primary endpoint:

• Change in appearance of the bladder mucosa (pre- and post-catheterization) (Δ), rated on a 4-point scale following visit 2.

Exploratory endpoints:

- Haematuria red blood cell count (RBC) at visit 2.
- White blood cell count (WBC) at visit 2.

Assessments

- Visual blood at cystoscopes and catheter Yes/No
- Pre-catheterization residual volume (ml)
- Haematuria red blood cell count (RBC)
- White blood cell count (WBC)

Urine volumes (mL)

Safety assessments:

- Adverse events
- Device deficiencies
- Concomitant medications

Population/subjects

A total of 50 subjects (healthy female volunteers) will be recruited in order to secure inclusion, randomization and completion of at least 40 subjects, assuming an approximate drop-out rate of 20%." The subjects will be recruited from a single center, American Health Research (AHR).

Inclusion/Exclusion Criteria:

	be included in the investigation a subject must comply the the following inclusion criteria:	Justification for inclusion criteria			
1.	Has given written informed consent	To ensure that the subject has been given written and oral information regarding the investigation and know enough about the investigation to decide on participation.			
2.	Is at least 18 years and have full legal capacity	To meet the Helsinki Declaration			
3.	Is female	The product is indicated for use with females			
4.	Has a negative urine Multistix dipstick test for erythrocytes (haematuria)	Haematuria could be a sign of urinary tract infection (UTI).			

A:	subject is not allowed to participate in case he/she:	Justification for exclusion criteria:
1,	Has used an internal urinary catheter or cystoscopy within the past month	To reduce potential bias from other events non-distinguishable from this study

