7.3 Safety Follow up

Adverse events and device deficiencies will be assessed at all visits, planned and unplanned. Subjects are followed through termination of the investigation (Visit 2). Any ongoing ADEs or SADEs at study termination will be followed until resolution. All subjects are encouraged to contact the Principal Investigator, or designee, if they experience problems that they believe are related to their investigational product or participation. This is to ensure that any device-related events are documented and to safeguard the subjects' health.

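### The two end categories of the causality scale in 20.7 rest on timing alone and mix device with procedures, so they overlap the middle categories and do not match the device-only ADE definition in 20.2

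*Combined protocol and SAP*

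**What the plan says.** Section 20.7 (Investigator's reporting responsibilities) introduces a five-level causality scale with the words "When reporting the SAE, the relationship to the test material shall be described whether the event is considered". The two end levels are:

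- *Definitely related/Causal relationship*: "the event has a temporal relationship with the test material use/application or procedures".
- *Not related*: "the event has no temporal relationship with the use of the test material or the procedures".

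The levels between them use other criteria. *Unlikely related* applies when "the relationship with the use of the test material seems not relevant and/or the event can be reasonably explained by another cause". *Possibly related* applies when "the relationship with the use of the test material is weak but cannot be ruled out"; it allows for alternative causes and takes in cases that cannot be assessed. *Probably related* turns on whether the link seems relevant or no other cause reasonably explains the event.

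Section 20.2 defines an adverse device effect as an adverse event tied to use of the investigational device, which "should be marked as related or possibly related on the adverse event form". It does not mention procedures.

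Two consequences follow from ADE status. Section 20.7 gives 10 days to report an ADE to the sponsor, and section 7.3 states that "Any ongoing ADEs or SADEs at study termination will be followed until resolution".

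**The concern.** A causality scale should demand more evidence as the claim gets stronger. Here the strongest level has the least demanding test, since timing suffices and no other cause has to be considered. At the other end, an event with an obvious separate cause cannot literally be called *Not related* if its timing fits.

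Both end levels also count a link to procedures, although the scale is presented as relationship to the test material. Every subject has two cystoscopies and one catheterisation. Only the catheter is randomised, so one of three instrumentations is the device under study. A scale that merges them cannot say which one an event belongs to.

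What is at stake is the labelling of device effects: SADE and USADE for serious events, and ADE for other events if the same scale is used for them.

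**Working it through.** The plan gives no figure to reproduce. The check sets the definitions beside each other and runs them against the visit schedule.

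**Step 1: criterion and object of each level (20.7)**

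| Level | Criterion | Object named |
|---|---|---|
| Not related | no temporal relationship | test material or procedures |
| Unlikely | link not relevant, and/or another cause | test material |
| Possibly | weak link, other causes possible | test material |
| Probably | link seems relevant, and/or no other reasonable cause | test material |
| Definitely | temporal relationship | test material or procedures |

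Both the criterion and the object change at the ends. The levels are therefore not steps on one scale, and they are not mutually exclusive.

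**Step 2: how close in time events must be (5.1, 7.2.2, 7.3, Table 7-1)**

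The catheterisation (V2-2), the void (V2-3), the second cystoscopy (V2-4) and the end of scheduled follow-up all belong to Visit 2. A visit lasts about 1 to 2 hours. Filling takes 6 cycles × 250 mL ÷ 50 mL/min = 30 minutes. That leaves at most 60 − 30 = 30 to 120 − 30 = 90 minutes for everything else in the visit, including drainage, both voids and the cystoscopy. Any event seen in the scheduled time after the catheter is close in time to it, so timing does little to separate causes.

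**Step 3: three example events**

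- *After the Visit 1 cystoscopy, before any catheter.* The event has a temporal relationship with a procedure, so it meets *Definitely* and fails *Not related*. No study catheter has been used, so *Unlikely* also fits and the event is not an ADE under 20.2. One event meets labels near opposite ends of the scale, and the top label contradicts 20.2.
- *After the catheter at Visit 2, with another reasonable cause* (for example the second cystoscopy). It meets *Definitely*, fails *Not related*, and also meets *Unlikely*.
- *After the catheter, with a weak link and other causes possible.* It meets both *Definitely* and *Possibly*.

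The text gives no rule for choosing when two levels apply.

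**Step 4: scope and labels**

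Section 20.7 asks the investigator to assess all events, serious or not, and to grade intensity for both, but it introduces the causality scale for SAEs only. Section 20.2 has two labels and 20.7 has five. *Possibly* appears in both. Nothing says whether *Probably* and *Definitely* together make up *related*, and the exclusion of *Unlikely* from ADEs has to be inferred.

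**Step 5: what depends on the label**

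| Consequence | Depends on relatedness? | Where |
|---|---|---|
| Entry of AEs in the database | No | 20.6 |
| SAE to sponsor within 24 hours | No | 20.7 |
| SAE to authorities within 7 days | No | 20.8 |
| Follow-up of SAEs | No | 20.5 |
| SADE/USADE label | Yes | 20.4.1, 20.4.3 |
| ADE label, 10-day reporting, follow-up after Visit 2 | Yes | 20.2, 20.7, 7.3 |
| Planned statistical comparison | None by relatedness | 10 |

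**The case against.** The strongest reply is that an investigator would not apply the end levels so literally. The top level carries the words *Causal relationship* in its name, and *Unlikely* and *Possibly* are open to any event with another explanation. This stands in part. A reader might infer that almost every event after the catheter becomes device-related, with none left as unrelated. The documents do not support that. Such events meet one definition and fail another, but they can still be graded *Unlikely*, which is not among the ADE labels in 20.2. The text leaves the grade to the investigator's reading and does not force the top one.

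A reader might also infer that this is a same-day study. It is not: participation is a period "which can be up to 3 days (if Day 0 and Day 1 are not on same day"), and the catheter is used at Visit 2, on Day 2. The narrower fact is that catheter use and the scheduled follow-up after it share one visit. Even that is not absolute, because section 7.3 also provides for unplanned visits and contact started by the subject.

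It can further be said that the scale is stated for SAEs only, in at most 50 healthy volunteers, and that SAE reporting and follow-up ignore relatedness. That is correct and limits the effect. The Medical Advisor's lists in 20.9 cover events related to the product or to the investigation, so separating device from procedure would not change them.

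Finally, a reader might infer that the device safety comparison loses its meaning. No such comparison is planned: section 10 has adverse events listed and/or summarised, and the wording is the same in both arms. Over-attribution is also the cautious error for reporting. However, the overlap can work in either direction, since the same event can be graded *Definitely* by one assessor and *Unlikely* by another.

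**Conclusion.** The point holds as a minor one. The end categories in 20.7 are defined by timing alone, they merge the study catheter with study procedures, they overlap the middle categories, and they conflict with the device-only ADE definition in 20.2. SADE and USADE labels can therefore be wrong. ADE labels, with their 10-day reporting and follow-up to resolution, can be wrong too if the scale is applied to all adverse events.

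SAE reporting to the sponsor and to authorities is unaffected, as is follow-up of SAEs, and no planned analysis rests on relatedness. No misclassification rate can be given, because the documents contain no event counts and do not say how an investigator would choose between overlapping categories.

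The conclusion assumes that the definitions are used as written. The adverse event form is not in the documents and may already separate device from procedure; the conflict between 20.2 and 20.7 would remain even then.

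**What to change.** - In 20.7, let *Definitely related* require a plausible temporal relationship and no other reasonable cause. Let *Not related* apply when there is no temporal relationship or when another cause clearly explains the event.
- Record relation to the study catheter separately from relation to the study procedures, if the adverse event form does not already do so, and name the same object in all five categories.
- State in 20.7 that the scale applies to all adverse events, serious or not.
- State in 20.2 which of the five categories make an event an ADE, replacing the two labels there.

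The cost is wording in two sections and at most one extra field on the adverse event form. No visits, staff or subjects are added.
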